6.1.5 Adjudication analyses

Additional outputs will be provided for the adjudicated tBPAR data. The outputs to be provided include a listing of the data and summary statistics table, the primary and supportive Bayesian analysis tables and corresponding figures, and the Kaplan Meier analysis. Adjudicated outputs will only be provided if all events can be assessed by the adjudication committee.

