3.2 Rationale for study design

The open-label, adaptive design selected for Part 1 of this prospective, multicenter study will allow for a cautious comparison and evaluation of the multiple dose CFZ533 safety, tolerability, PK and PD as added to MMF + Tac and CS for 3 months. Part 2 expands upon the knowledge gained in Part 1 to assess the clinical activity and exposure-response of CFZ533 in a well powered CNI-free treatment regimen with basiliximab induction + MMF and CS for initial and maintenance prophylaxis of organ rejection in adult *de novo* renal transplant recipients.

Corporate Confidential Information

Although the ideal study would employ a double-blind, double-dummy methodology to minimize bias, in consideration of the inherent complexity of this adaptive study (multiple arms, frequent visits, interim analysis and extensive investigations), it has been decided to utilize an open-label design. This open-label design will not only minimize the risks for patients during the initial investigation of CFZ533 should the need for rapid intervention arise, such as emergent SAEs, but it also avoids the additional difficulties and

errors associated with sham-dose adjustments for a Tac placebo in CFZ533 arms and placebo injections/infusions in the control group. It is recognized that Investigator bias can affect the management of patients receiving investigational treatment; especially in an open-label study setting. In general, such scrutiny biases the study in favor of the control arm. As such, efforts to minimize bias for or against the CFZ533 treatment arms will be managed through the use of a limited number of high-quality transplant centers with a similar standard of care and patient management. In order to overcome any bias introduced by the open-label design, in Part 2, a blinded external independent adjudication committee (AC) has been formed to centrally evaluate all biopsies taken for suspected rejection reactions and other kidney disease related events in an unbiased, standardized and blinded manner. Adjudication outcome will be entered into the eCRF and additional outputs provided.

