8.5 Adjudication Committee

Not required for Part 1.

Since the study is open-label for investigators, for Part 2 an independent and blinded Adjudication Committee (AC) has been appointed in order to centrally evaluate all events reported as acute rejection, delayed graft function or other kidney dysfunction in an unbiased manner.

Details on the working procedures of the AC are described in a separate AC charter. An additional supportive PD analysis will be performed for BPAR and tBPAR based on adjudicated results.

9 Data analysis

Data from Part 1 and Part 2 will be presented separately.

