9.5 Analysis of secondary and exploratory variables

9.5.1 Efficacy

Other efficacy variables will be analyzed similarly to the primary efficacy endpoint, although without the non-inferiority test:

- tBPAR at Months 3, 6 and 12
- BPAR at Months 3, 6 and 12
- Graft loss at Months 6 and 12
- Death at Months 6 and 12
- Graft loss or death at Months 6 and 12
- Antibody mediated tBPAR at Month 12

For each of the efficacy endpoints (primary and secondary), simple event rate estimates (proportion of events) will be obtained and each CFZ533 treatment arm event rate will be compared with the control arm event rates using Z-statistics based on two-sided 95% confidence intervals for differences in event rates.

As supportive analyses, BPAR and tBPAR will also be analyzed using the adjudicated results.

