The same outputs and presentations of the results as for the primary analysis will be provided. The analysis will be repeated for the adjudicated data when applicable.

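### SAP 6.1.5 makes the adjudicated tBPAR outputs depend on every event being assessable, a condition the protocol does not contain (minor)

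*SAP*

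**What the plan says.** The SAP and the protocol treat the adjudicated analyses differently.

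- **SAP 6.1.5** begins "Additional outputs will be provided for the adjudicated tBPAR data". It lists what these are: a listing, a summary table, the primary and supportive Bayesian analyses with figures, and the Kaplan-Meier analysis. It then ends "Adjudicated outputs will only be provided if all events can be assessed by the adjudication committee".
- **SAP 6.1.4**, on the supportive Poisson-based analysis, says "The analysis will be repeated for the adjudicated data when applicable".
- **Protocol 3.2** introduces the committee with the words "In order to overcome any bias introduced by the open-label design, in Part 2, a blinded external independent adjudication committee". Its task is to "centrally evaluate all biopsies taken for suspected rejection reactions and other kidney disease related events", and the section says that outputs will follow.
- **Protocol 8.5** says "An additional supportive PD analysis will be performed for BPAR and tBPAR based on adjudicated results".
- **Protocol 9.5.1** says "As supportive analyses, BPAR and tBPAR will also be analyzed using the adjudicated results".

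None of the three protocol sections attaches a condition. The SAP gives no reason for its condition and no rule for an event that the committee cannot assess. It also does not say whether the condition applies to the whole trial or to each cut-off.

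**The concern.** Part 2 is open-label, and protocol 3.2 offers blinded central review as its answer to the resulting bias. Under protocol 6.5.1, local reads may use Banff 2009 or Banff 2013, and borderline findings are judged by local practice and count as tBPAR if treated. The adjudicated outputs are the planned check on whether the tBPAR result depends on those local reads.

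An all-or-nothing rule lets a single poor or missing specimen remove that check entirely. Whether it is removed would be known only after events have occurred, in a trial whose core team is unblinded (protocol 5.4). With 30 and 15 patients, one reclassified event can move the tBPAR result across the success threshold.

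**Working it through.** **1. Text comparison.** The main point rests on no figure. The protocol makes three unconditional commitments (3.2, 8.5, 9.5.1). The SAP makes one conditional commitment (6.1.5). As written they cannot both be followed if any event is unassessable.

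**2. Inputs from the plan.** Arms of 30 and 15. Priors Beta(1/3, 1/3) for CFZ533 and Beta(1, 13) for control. Success if Pr(difference < 0.20) > 60%. The plan's own figures reproduce: Beta(1, 13) has mean 7.1% and 95% interval 0.2% to 24.7% (stated 7%; 0.2%, 24%). The N = 30 row of SAP Table 1-1 also holds, with Pr(θ > 0.20) = 0.904 at 9/30 and 0.812 at 8/30.

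**3. How close one event is to the threshold.** Posteriors are Beta(1/3 + r, 1/3 + 30 − r) and Beta(1 + c, 13 + 15 − c), for r CFZ533 events and c control events.

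| Control events c | Pr at limit | Pr one event above |
|---|---|---|
| 0 | r = 6: 0.656 | r = 7: 0.495 |
| 1 | r = 7: 0.642 | r = 8: 0.496 |
| 2 | r = 8: 0.633 | r = 9: 0.498 |

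For c ≥ 3 the limit stays at b = 8, because 9/30 meets the termination count. So b = 6, 7, 8 for c = 0, 1, ≥ 2.

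**4. Chance of being exactly at the limit.** This is the sum over c of Bin(c; 15, p0) × Bin(b; 30, p1). The true rates are assumed.

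| p1 vs p0 | c = 0 | c = 1 | c = 2 | c ≥ 3 | Total |
|---|---|---|---|---|---|
| 7% vs 7% | 0.0041 | 0.0012 | 0.0001 | 0.0001 | 0.0055 |
| 15% vs 7% | 0.0461 | 0.0315 | 0.0084 | 0.0035 | 0.0894 |
| 20% vs 7% | 0.0604 | 0.0585 | 0.0221 | 0.0092 | 0.1502 |

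**5. Chance of losing the outputs.** Let q be the chance that an event cannot be assessed. It is assumed to be 1-10%, independent between events and applied to local tBPAR events. Loss = 1 − (1 − q·p1)^30 × (1 − q·p0)^15. This gives 3.1-27.1% (7% vs 7%), 5.4-42.8% (15% vs 7%) and 6.8-50.9% (20% vs 7%).

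**6. Both together.** Multiply each cell in step 4 by 1 − (1 − q)^(b + c). For 20% vs 7% and q = 10%:

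- c = 0: 0.0604 × (1 − 0.9^6) = 0.0604 × 0.469 = 0.0283
- c = 1: 0.0585 × (1 − 0.9^8) = 0.0585 × 0.570 = 0.0333
- c = 2: 0.0221 × (1 − 0.9^10) = 0.0221 × 0.651 = 0.0144
- c ≥ 3: 0.0092 × about 0.69 = 0.0064
- Sum: 0.0824

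Over q = 1-10% the joint chance is 0.04-0.3% (7% vs 7%), 0.6-4.7% (15% vs 7%) and 1.1-8.2% (20% vs 7%).

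**7. What the joint figure does not show.** At the limit, success is overturned by one added CFZ533 event, or, when c is 1 or 2, by one removed control event (7/30 vs 1/15 at 0.642 becomes 7/30 vs 0/15 at 0.495; 8/30 vs 2/15 at 0.633 becomes 8/30 vs 1/15 at 0.496). An added CFZ533 event would be a locally negative episode upgraded centrally, which step 5 does not count. Removing a locally counted CFZ533 event only moves the result further into success. The direct link is therefore an unassessable control event with c = 1 or 2. For 20% vs 7% its chance is 0.0585·q + 0.0221·[1 − (1 − q)²], which is 0.10% at q = 1% and 1.0% at q = 10%. For 15% vs 7% it is 0.0315·q + 0.0084·[1 − (1 − q)²], about 0.05-0.5%.

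**The case against.** The strongest reply is that the sentence is a sequencing rule. SAP 6.1.4 works with successive cut-offs at Months 3 and 6 and repeats the analysis for adjudicated data only when that applies. In that setting 6.1.5 may simply prevent a half-adjudicated endpoint from being reported. This reading is plausible, and the committee charter, which is not among the documents, may deal with unassessable events. But the sentence speaks of events that can be assessed, not of a review that is finished. If sequencing is the intent, saying so costs nothing.

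Second, SAP 1.2 cites protocol v02 (Amendment 02, 11 April 2016) and SAP 1.4.1 describes three parts, while the protocol at hand has two. The SAP may not have been written against the present protocol wording. That may explain the mismatch, but the two texts still need to be reconciled.

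Third, the analysis is supportive. Local histology is already read blind (protocol 6.5.1), and adjudication does not undo site decisions to suspect or treat a rejection. This stands and limits the severity.

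Two stronger readings are tempting but not supported:

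- Protocol 8.5 gives the committee "all events reported as acute rejection, delayed graft function or other kidney dysfunction", so a reader might infer that an unassessable delayed-graft-function referral would also block the outputs. The SAP paragraph concerns adjudicated tBPAR data, so its events are most naturally the rejection events behind those outputs.
- SAP 6.1.5 names tBPAR only, so a reader might infer that adjudicated BPAR was dropped. Table 6-1 is not shown and nearby text is blacked out, so this can only be a point to confirm.

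**Conclusion.** The contradiction is real and minor. SAP 6.1.5 states a condition that three protocol sections do not, and read literally it lets one unassessable event remove every adjudicated tBPAR output. The formal proof-of-concept criterion does not use these outputs and is unaffected.

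A reader might take the loss figures in step 5, up to about 51%, as the size of the problem. They are not. They rest on an assumed unassessable rate and on the literal reading, and in most of those cases the result would not be close. The joint figures, at most 8.2% across the assumed scenarios, are the better guide, and they too are generous. In most of those cases the result would turn on an added CFZ533 event that the model does not count, and the directly linked part is at most about 1.0%. Applying SAP Table 1-1 after every patient (also an assumption) would lower the at-limit chances from 15.0%, 8.9% and 0.6% to about 9.2%, 5.8% and 0.4%.

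**What to change.** Replace the last sentence of SAP 6.1.5 with:

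> *Adjudicated outputs will be produced as supportive analyses once the committee has completed its review for the cut-off. The number of reported rejection episodes the committee could not assess will be given by arm, and the adjudicated tBPAR analysis will be shown with those episodes classified least and most favourably to CFZ533 (counted as tBPAR only if anti-rejection treatment was given).*

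Also confirm that adjudicated BPAR, promised in protocol 8.5 and 9.5.1, is covered, and reconcile the SAP with the current protocol version.

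Two bounding runs are needed because one can mislead. Take 7/30 vs 1/15 with one unassessable local event in each arm. As read locally the posterior probability is 0.642. The least favourable classification (7/30 vs 0/15) gives 0.495 and the most favourable (6/30 vs 1/15) gives 0.775. Removing both events together (6/30 vs 0/15) gives 0.656 and would hide the failure.

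The cost is one replaced passage and two extra supportive runs. The committee and its reads are already planned.

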6.2 Secondary and exploratory objectives

6.2.1 Variables

Composite failure is a secondary variable where patients are defined to be failures if they experience any one of the following events

tBPAR

graft loss

death

Corporate Confidential Information

A date is defined for all events (e.g. borderline rejection, acute rejection) on the rejection level. In case of several events of the same type (e.g. two acute rejections) the earliest will be chosen for the analysis on the patient level.

The main part of the information for the efficacy evaluation comes from the Rejection eCRF page as well as the Biopsy eCRF page. For the derivation of the efficacy variables the

information from both pages need to be merged. The Rejection eCRF page is linked with the Biopsy eCRF page by the date of the (first) biopsy. Follow-up biopsies of the same rejection episode may be taken and are linked with the first biopsy by the date.

Borderline rejection

A biopsy is considered ‘borderline’ if, from the Biopsy eCRF page based on the pathologist’s assessment, “Borderline changes = Yes” on the Biopsy eCRF page.

Acute rejection

Acute rejections are identified in the database from the Rejection eCRF page. One of the following conditions must be met:

- Primary final clinical diagnosis indicates an acute rejection (either “acute rejection” or “acute and chronic rejection”)
- OR Antibody mediated rejection = “Yes” from the Kidney allograft biopsy eCRF page
- OR Acute T-cell mediated rejection = “Yes” from the Kidney allograft biopsy eCRF page

The date of event is the “Date rejection was first suspected” from Rejection eCRF page, or if missing the date of the first biopsy of the particular rejection episode.

Treated acute rejection

Treated acute rejections are a subset of acute rejections.

A treated acute rejection is defined if the following criteria are fulfilled:

- Acute rejection and
- “Was anti-rejection therapy administered = Yes” from the Rejection eCRF page.

The date of event is the “Date rejection was first suspected” from Rejection eCRF page, or if missing the date of the first biopsy of the particular rejection episode.

Treatments for acute rejection will be categorized into 3 groups: Steroids, Antibodies, and Other using the CRF information from the Rejection eCRF page (Were steroids administered? Was antibody treatment administered?).

Biopsy-proven acute rejection (BPAR)

A rejection is considered a biopsy-proven acute rejection if the following criterion is fulfilled:

“Acute T-cell mediated rejection = Yes” or “Antibody mediated rejection = Yes” or Borderline changes = “Yes” from the Biopsy eCRF page

The date of event is the “Date rejection was first suspected” from corresponding Rejection eCRF page, or if missing the date of the first biopsy of the particular rejection episode.

The BPAR episode can be classified into rejection types: t-cell mediated, antibody mediated, or a combination of those.

Acute antibody-mediated rejection (AMR)

A rejection is identified as an antibody-mediated rejection (also known as humoral rejections) if the following criterion is fulfilled:

- “Antibody mediated rejection = Yes” from the Biopsy eCRF page

The date of event is the “Date rejection was first suspected” from Rejection eCRF page, or if missing the date of the first biopsy of the particular rejection episode.

Treated biopsy-proven acute rejection (tBPAR)

Treated biopsy-proven rejections are a subset of biopsy-proven acute rejections.

A treated biopsy-proven acute rejection is defined if the following criteria are fulfilled:

- Biopsy-proven acute rejection and
- “Was anti-rejection therapy administered = Yes” from the Rejection eCRF page.

The date of event is the “Date rejection was first suspected” from Rejection eCRF page, or if missing the date of the first biopsy of the particular rejection episode.

Note that careful data cleaning is necessary to align the answer to “Was anti-rejection therapy administered?” with the concomitant medication eCRF page.

Steroid-treated biopsy proven acute rejection

Steroid-treated biopsy proven acute rejections are a subset of treated biopsy proven acute rejections. A steroid-treated biopsy proven acute rejection is defined if the following criteria are fulfilled:

- Treated biopsy proven acute rejection and
- “Were steroids administered = Yes” on the Rejection eCRF.

The date of event is the “Date rejection was first suspected” from Rejection eCRF page, or if missing the date of the first biopsy of the particular rejection episode.

Steroid-resistant biopsy proven acute rejection

Steroid-resistant biopsy proven acute rejections are a subset of steroid-treated biopsy proven acute rejections. A steroid-resistant biopsy proven acute rejection is defined if the following criteria are fulfilled:

- Steroid-treated biopsy proven acute rejection and
- “Was the rejection steroid resistant? = Yes” from the Rejection eCRF page

The date of event is the “Date rejection was first suspected” from Rejection eCRF page, or if missing the date of the first biopsy of the particular rejection episode.

Antibody-treated biopsy proven acute rejection

Antibody-treated biopsy proven acute rejections (BPAR with T-cell depleting therapy) are a subset of treated biopsy proven acute rejections. It is a clinically significant sub-component of treated BPAR as a marker of severity. An antibody-treated biopsy proven acute rejection is defined if the following criteria are fulfilled.

- Treated biopsy proven acute rejection and
- “Was antibody treatment administered = Yes” from the Rejection eCRF page

The date of event is the “Date rejection was first suspected” from Rejection eCRF page, or if missing the date of the first biopsy of the particular rejection episode.

Sub-clinical biopsy proven acute rejection

A sub-clinical biopsy proven acute rejection is defined as a BPAR *without* clinical suspicion of a rejection i.e. a biopsy was performed without the suspicion of an acute rejection (e.g. center-driven local-routine biopsy, protocol driven biopsy, etc.) but the result of that biopsy shows histological evidence of an acute rejection (Banff classification):

- BPAR and
- “Clinical suspicion of an acute rejection = No” on the Kidney Allograft Rejection eCRF or Reason for biopsy = “Routine biopsy per local practice” from the Biopsy page..

The date of event is the date of biopsy.

Graft Loss (GL)

The allograft will be presumed to be lost based on whichever of the following occurs first: the day the patient starts dialysis and is not able to subsequently be removed from dialysis, the day of transplantectomy, or the day irreversible loss of graft perfusion is demonstrated by appropriate imaging techniques. Primary graft non-function is a subset of graft loss.

A patient will be considered to have graft loss if in the Graft Loss eCRF page the following condition is met:

- “Has subject suffered a graft loss = Yes”

The date of graft loss is specified on the Graft Loss eCRF page. The date returned to regular dialysis or date of transplantectomy will be used if earlier.

Death

The endpoint death is derived from the Death eCRF page where also the date of death is captured.

Corporate Confidential Information

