6.5 Efficacy / Pharmacodynamic assessments

6.5.1 Efficacy assessments

Treated Biopsy Proven Acute Rejection (tBPAR)

A treated BPAR is any condition where the subject received anti-rejection treatment and was histologically diagnosed as acute rejection (according to the Banff 2009 criteria, [Appendix 8](#) or the Banff 2013 criteria. Borderline histological findings are interpreted according to local medical practice and fulfill the criteria of tBPAR if anti-rejection treatment is given). Renal biopsies will be collected for all cases of suspected acute rejection.

Kidney allograft biopsy

For all suspected rejection episodes, regardless of initiation of anti-rejection treatment, an allograft biopsy must be performed according to local practice preferably within 48 hrs. Biopsies will be read by the local pathologist according to the updated Banff 2009 criteria ([Appendix 8](#), or the Banff 2013 criteria depending on the local practice). The results of the biopsy read by the local pathologist will be listed on the Kidney Allograft Biopsy eCRF. The results will be used for subject management for acute rejection. The local pathologist will remain blinded to treatment. Any biopsies performed according to local practice (e.g., not for cause) should also be recorded. In Part 2, biopsies performed for suspected rejection and other kidney disease related events will also be evaluated centrally by an independent Adjudication Committee.

Graft loss

The allograft will be presumed to be lost on the day the subject starts dialysis and is not able to subsequently be removed from dialysis. If the subject undergoes allograft nephrectomy prior to starting permanent dialysis, then the day of nephrectomy is the day of graft loss. The reason for graft loss will be recorded on the Graft Loss eCRF. This will be reported on the Study Completion eCRF and Treatment Phase Disposition eCRF with Graft Loss as the reason for study discontinuation and on the appropriate Dosage Administration Record eCRF(s) if death occurs while on randomized treatment. Graft loss is considered a SAE and should be reported on the Adverse Event eCRF (as serious) and the SAE reported to the local Novartis Drug Safety and Epidemiology Department local Novartis Drug Safety and Epidemiology (DS&E) Department within 24 hrs.

Death

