- Antibody-mediated rejection – due to circulating anti-donor antibodies, C4d, and allograft pathology:
 - C4d deposition without morphologic evidence of acute rejection – C4d, anti-donor antibodies, no signs of acute or chronic rejection, no ATN-like minimal inflammation.
 - Acute antibody-mediated rejection – C4d, anti-donor antibodies, and acute tissue injury, such as: (“suspicious for” if antibody not demonstrated)
 - Type I – ATN-like minimal inflammation
 - Type II – Capillary involvement and/or thromboses
 - Type III – Arterial changes
 - Chronic antibody-mediated rejection – evidence of chronic tissue such as glomerular double contours, peritubular capillary basement membrane multilayering, interstitial fibrosis/tubular atrophy (IFTA), or fibrous intimal thickening in arteries. Borderline changes “suspicious” for acute T cell-mediated cellular rejection. No intimal arteritis present, but there are foci of mild tubulitis with mild interstitial infiltration. Threshold for rejection diagnosis is not met.
 - T cell mediated rejection
 - Type IA - Significant interstitial infiltration (> 25% of parenchyma) and foci of moderate tubulitis (> 4 mononuclear cells/tubular cross section or group of 10 tubular cells).
 - Type IB - Significant interstitial infiltration (> 25% of parenchyma) and foci of severe tubulitis (> 10 mononuclear cells/tubular cross section or group of 10 tubular cells).
 - Type IIA - Mild to moderate intimal arteritis
 - Type IIB - Severe intimal arteritis comprising > 25% of the luminal area
 - Type III - Transmural (full vessel wall thickness) arteritis and/or arterial fibrinoid change and necrosis of medial smooth muscle cells (with accompanying lymphocytic inflammation)
 - Interstitial fibrosis and tubular atrophy**
 - Grade I - Mild interstitial fibrosis and tubular atrophy without (a) or with (b) specific changes suggesting chronic rejection
 - Grade II - Moderate interstitial fibrosis and tubular atrophy (a) or (b)
 - Grade E III - Severe interstitial fibrosis and tubular atrophy and tubular loss (a) or (b)

- Other: Changes not considered to be due to rejection (e.g., post-transplant lymphoproliferative disorder, nonspecific changes, acute tubular necrosis, etc.), specifically:
 - Chronic hypertension - Arterial/fibrointimal thickening with reduplication of elastica, usually with small artery and arteriolar hyaline changes.

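### SAP 6.2.1 counts untreated borderline biopsies as BPAR, and no visible run of the Month 3 criterion leaves out treated borderline cases

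*SAP*

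**What the plan says.** The BPAR definition in SAP 6.2.1 begins "A rejection is considered a biopsy-proven acute rejection if the following criterion is fulfilled". It then lists T-cell-mediated rejection, antibody-mediated rejection, "or Borderline changes = “Yes” from the Biopsy eCRF page". Treatment plays no part. tBPAR is built on top of it: "Treated biopsy-proven rejections are a subset of biopsy-proven acute rejections", with the added condition that anti-rejection therapy was given.

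Other parts of the same section do not follow this. Acute rejection requires that "Primary final clinical diagnosis indicates an acute rejection", or that the biopsy shows antibody-mediated or T-cell-mediated rejection; borderline is not a criterion. Treated acute rejection inherits that ("Treated acute rejections are a subset of acute rejections"). For BPAR types, "The BPAR episode can be classified into rejection types: t-cell mediated, antibody mediated, or a combination of those"; there is no class for a borderline-only episode.

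In the protocol, Section 6.5.1 states the trial's rule for the primary endpoint: "Borderline histological findings are interpreted according to local medical practice and fulfill the criteria of tBPAR if anti-rejection treatment is given". Appendix 8, which Section 6.5.1 cites, describes borderline changes with the words "Threshold for rejection diagnosis is not met". Section 9.5.1 lists BPAR at Months 3, 6 and 12 and compares its rate between arms.

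**The concern.** Two things are at stake, and they should be kept apart.

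The first is BPAR, a secondary endpoint. As the SAP is written, histology that the protocol's own appendix places below the rejection threshold is counted as biopsy-proven rejection, even where nobody treated it. A borderline-only episode without a clinical diagnosis of acute rejection is then BPAR but not acute rejection, and it has no BPAR type. A programmer cannot resolve that from the text.

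The second is the Month 3 proof-of-concept criterion, which rests on tBPAR. There, a borderline finding becomes an event only through a decision to treat. That decision is local (Protocol 6.5.1) and made with knowledge of the arm (Protocol 5.4). Protocol 3.2 itself expects investigator scrutiny to favour control. Treated borderline cases are thus the part of the primary endpoint most exposed to the open-label design, and it is reasonable to want to see the result without them.

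**Working it through.** **Step 1. The definitions side by side.**

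| Patient | SAP acute rejection | SAP BPAR | SAP tBPAR | Protocol 6.5.1 tBPAR |
|---|---|---|---|---|
| T-cell- or antibody-mediated, treated | yes | yes | yes | yes |
| Borderline only, treated | only if the clinical diagnosis says so | yes | yes | yes |
| Borderline only, untreated | only if the clinical diagnosis says so | yes | no | no |

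The SAP and protocol agree on tBPAR in every row. The misfit is in the BPAR column, last row.

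**Step 2. Effect on BPAR.** With 30 and 15 patients (Protocol 3.1.4), each patient who is BPAR only through an untreated borderline biopsy adds 1/30 = 3.3 percentage points in the CFZ533 arm or 1/15 = 6.7 in control.

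**Step 3. The proof-of-concept boundary.** Inputs: priors Beta(1/3, 1/3) for CFZ533 and Beta(1, 13) for control, and success if Pr(difference < 0.20 | data) > 0.60 (SAP 6.1.3). With r of 30 and c of 15 events the posteriors are Beta(1/3 + r, 1/3 + 30 − r) and Beta(1 + c, 13 + 15 − c). The probability was found by numerical integration.

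The plan's own figures come out first. All 28 rows of SAP Table 1-1 reproduce. Success needs at most 6, 7 or 8 CFZ533 events when control has 0, 1 or 2 (0.656, 0.642 and 0.633), and it fails at 7, 8 and 9 (0.495, 0.496 and 0.498). These are the Part 2 termination counts in Protocol Appendix 3: 7, 8 and 9. With 3 or more control events, the count of 9 comes from the stopping rule instead: Pr(rate > 0.20) is 0.904 at 9/30 and 0.812 at 8/30.

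Now change one event, supposing it to be a treated borderline-only case:

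| CFZ533 | Control | Posterior means | Difference in means | Pr(difference < 0.20) | Criterion |
|---|---|---|---|---|---|
| 7/30 | 1/15 | 7.333/30.667 = 0.239; 2/29 = 0.069 | 0.170 | 0.642 | met |
| 8/30 | 1/15 | 8.333/30.667 = 0.272; 2/29 = 0.069 | 0.203 | 0.496 | not met |
| 8/30 | 2/15 | 8.333/30.667 = 0.272; 3/29 = 0.103 | 0.168 | 0.633 | met |

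One case in the CFZ533 arm turns met into not met; one in control turns it back.

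**Step 4. What a borderline share could do on average.** The documents give no rate, so these are assumptions: non-borderline tBPAR of 15% on CFZ533 and 7% on control, with treated borderline cases added on top. The probability of progressing was summed exactly over Binomial(30) × Binomial(15), with the stopping rule applied at n = 30.

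| Treated borderline added | CFZ533 only | Both arms |
|---|---|---|
| 0 points | 0.91 | 0.91 |
| 5 points | 0.74 | 0.80 |
| 10 points | 0.50 | 0.62 |

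Applying the stopping rule patient by patient lowers all of these (0.80 with no borderline; 0.59 and 0.62 at 5 points; 0.37 and 0.43 at 10 points) but keeps the pattern.

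**The case against.** The best reply is that the primary endpoint is exactly what the protocol prespecified. That stands. A reader might infer from the BPAR wording that any borderline biopsy counts towards proof of concept, or that the SAP departs from the protocol on its primary endpoint. Neither is so: tBPAR needs anti-rejection therapy, and Protocol 6.5.1 says the same.

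A reader might also infer that nothing checks the borderline cases. That is too strong. The local pathologist is blinded (Protocol 6.5.1), a blinded committee reviews events centrally (Protocol 8.5), and the main tBPAR analyses are to be repeated on adjudicated data (SAP 6.1.5). SAP 6.2.1 also defines borderline rejection and treated acute rejection, which may appear in the frequency tables of Table 6-1; that table is not in the public text. These checks are partial. Adjudication rereads the biopsy but does not undo the decision to treat, its outputs appear only if every event can be assessed, and a frequency table would not give the posterior probability.

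On BPAR, the visible protocol gives no separate definition, so the SAP contradicts no explicit BPAR rule, and Appendix 8 is a general histological classification. The criterion also speaks of a rejection, which may keep some borderline biopsies out. But the sub-clinical category in SAP 6.2.1 admits routine biopsies without clinical suspicion, and the mismatch with the SAP's own acute-rejection definition remains.

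Finally, with 30 and 15 patients any single event, borderline or not, reverses a result at the boundary. That is right: Step 3 shows that borderline cases can matter, not that they will.

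**Conclusion.** The point holds as a small one. Secondary BPAR is inflated by every untreated borderline-only patient, at 3.3 points each on CFZ533 and 6.7 each in control, and the definition does not fit Appendix 8 or the rest of SAP 6.2.1. The tBPAR definition should stay. What is missing is a proof-of-concept run, in the visible text, without borderline-only cases. One such case in either arm is enough to reverse the outcome at the boundary (0.64, 0.50 and 0.63 in Step 3).

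This assumes full enrolment at 30 and 15. How often borderline cases would arise, and in which arm, cannot be judged from the documents, nor is it stated whether the historical events behind Beta(1, 13) include them. A reader might infer that counting treated borderline cases favours CFZ533. The documents do not support that: cases in the CFZ533 arm make success harder and cases in control make it easier. If scrutiny does favour control, as Protocol 3.2 expects, the present definition is the stricter one for CFZ533.

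**What to change.** In SAP 6.2.1:

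- Define BPAR as T-cell-mediated or antibody-mediated rejection, and report borderline as its own class.
- Define tBPAR separately as T-cell-mediated rejection, antibody-mediated rejection or borderline changes, with anti-rejection therapy given. It then still matches Protocol 6.5.1. The sentence making tBPAR a subset of BPAR has to go; if it stayed, the narrower BPAR would remove treated borderline cases from the primary endpoint. Admitting borderline to BPAR only when treated is no better, because BPAR would then depend on the open-label decision to treat.
- State for each derived category (steroid-treated, steroid-resistant, antibody-treated, sub-clinical) which of the two definitions it builds on.

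In SAP 6.1.4, pre-specify one run of the Month 3 posterior criterion with borderline-only tBPAR excluded in both arms, on local readings and, where available, adjudicated readings. Label it supportive: it may look more favourable to CFZ533 than the primary result and should not replace it. The stopping counts are not touched.

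The cost is SAP wording and one extra table from fields already on the Biopsy and Rejection eCRF pages. There will be fewer BPAR events, and because tBPAR could then exceed BPAR, the tables need a footnote saying why.
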